**2.B.8 Depression is Linked to Poor Outcomes in Heavy Drinkers.** [As predicted by the ANA, heavy drinkers (n=42, EtG > 499 ng/mL) with a major depressive disorder attained an average of 1 EtG-negative urine sample during treatment (SE=2.2), whereas non-depressed participants averaged 5.6 consecutive EtG-negative samples (SE=1.5; p<0.05). Among heavy drinkers in CM (n=16), those with depression attained less abstinence than non-depressed participants. The difference was not statistically significant, likely due to insufficient power. Notably, **depression was not associated with alcohol abstinence in light drinkers**. These findings support our premise that ANA domains can predict alcohol abstinence in heavy drinkers.]

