**Aims 1 and 2.** Recent alcohol use will be documented by using urine test results (binary outcome: EtG < 100 ng/mL or EtG > 100 ng/mL) and analyzed by using generalized estimating equations (GEE), generalized regression, and Cox proportional hazard regression techniques. Other outcome measures will be derived from recent alcohol use, such as 1) alcohol use (yes/no) over time; 2) longest duration of abstinence; 3) total number of periods of alcohol abstinence; 4) time to first alcohol abstinence; and 5) time to relapse after a specified period of alcohol abstinence. These outcomes will be examined across CM condition, time, and the CM condition-by-time interaction to determine whether one condition is superior to the others in promoting discontinuation of alcohol use. Additional analyses will be conducted by defining alcohol use in various clinically descriptive ways, such as the mean number of heavy drinking days or heavy drinking months across groups. Group comparisons of other Aim 2 outcomes will be assessed and evaluated in a similar fashion (e.g., longest duration of drug abstinence, mean HIV risk score).

Analyses will be conducted on the intent-to-treat sample (n=240). This is a conservative approach aimed at avoiding overestimation of the treatment effect. It includes all participants who were randomly assigned to treatment conditions, regardless of treatment completion. GEE models will be used to evaluate the differential change in primary and secondary outcomes by study condition over the 12-month study period (1 month before the baseline interview plus the 1-month induction, 4-month treatment, and 6-month follow-up periods), and whether condition interacts with change over time. This approach allows us to characterize between-group differences in longitudinal outcomes. We hypothesize that the modified interventions (High-Magnitude CM and Shaping CM) will lead to higher rates of alcohol abstinence than the Usual CM intervention. If the condition-by-time interaction variable is significant, we will conduct planned comparisons to examine the hypothesized pattern for each outcome. Such an approach will allow us to test this set of hypotheses with specificity. We will also conduct a direct comparison of the High-Magnitude CM group and the Shaping CM group.

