**[Aim 4.]** We will examine whether the ANA moderators (executive functioning, negative emotionality, alcohol-related incentive salience) interact with CM, and if so, with which CM condition. This will help us determine whether a given moderator significantly modified the impact of CM on alcohol abstinence. First, we will create an interaction term of CM condition by the moderator in question and examine whether the interaction is significant. Second, if the interaction is significant, we will examine whether the outcome varies within each CM condition across 3 categories of the moderator in question: 1) Mean  $\pm 1$  standard deviation, 2)  $> 1$  standard deviation, and 3)  $< 1$  standard deviation. This will be accomplished by conducting a planned linear trend analysis or simple effects analysis for each CM condition, since we hypothesize that, for example, more executive dysfunction will produce worse treatment outcomes. Although we anticipate that this association will hold true for each condition, we also hypothesize that the effect will be more pronounced in the Usual CM condition. If appropriate for a clearer clinical interpretation, we will use centering (i.e., subtracting the mean from all participant values on the measure) on the moderator being examined, which is consistent with current expert recommendations.

**Missing Data.** We have developed extensive tracking procedures to reduce missing data, which will be handled in a manner consistent with current expert recommendations. We will use maximum likelihood or multiple imputation and extensive sensitivity analyses, including “missing not at random” approaches, to examine the robustness of treatment effects under varying assumptions. These approaches are preferable to other data imputation approaches, such as mean imputation.

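### Time to relapse is undefined for participants who never become abstinent, so the planned between-arm test of it rests on a post-randomization subset and conflicts with the intent-to-treat sample of 240

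*Combined protocol and SAP*

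**What the plan says.** Section 4.G.2 (Aims 1 and 2) derives five measures from the EtG results. The fifth is "time to relapse after a specified period of alcohol abstinence". The named methods are "generalized estimating equations (GEE), generalized regression, and Cox proportional hazard regression techniques", with no statement of which model serves which measure. The purpose is comparative: "These outcomes will be examined across CM condition, time, and the CM condition-by-time interaction to determine whether one condition is superior to the others".

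The following paragraph sets the population: "Analyses will be conducted on the intent-to-treat sample (n=240"). It adds: "It includes all participants who were randomly assigned to treatment conditions, regardless of treatment completion". It also states the expected direction: the modified conditions "will lead to higher rates of alcohol abstinence than the Usual CM intervention".

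The Missing Data paragraph of the same section says "We will use maximum likelihood or multiple imputation and extensive sensitivity analyses". The plan does not give the length of the abstinence period, the time origin, the definition of relapse, or how a participant who never meets the abstinence criterion enters this outcome.

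**The concern.** A participant who never reaches the specified abstinence has no starting point for time to relapse and cannot enter a Cox risk set. Unless a rule is added, the people compared are those who attained abstinence after randomization. The trial expects the arms to differ on that very event, so randomization no longer guarantees that the compared groups are alike.

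The protocol also gives a reason to expect a particular imbalance. Aim 4 in the Specific Aims hypothesizes that executive dysfunction, negative emotionality and alcohol-related incentive salience lower abstinence in every condition, and that people high on these traits respond better to modified CM than to Usual CM. If that is right, the additional attainers in the modified arms are the harder cases. If harder cases also relapse sooner, the more effective arm will look worse on this measure. The risk is that a selection effect is reported as a treatment effect on relapse.

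**Working it through.** **What the plan supplies.** It gives no event count, hazard ratio or power for time to relapse, so there is no figure to reproduce. It does give:
- 240 randomized to three arms, so 80 per arm; power is based on 180, or 60 per arm, after 25% attrition (4.G.3);
- alpha 0.05 (4.G.1; two-sided is assumed here);
- EtG three times a week in weeks 9-20 and three times in follow-up (4.F.2), at weeks 25, 33 and 47 (4.F.1);
- pilot evidence that a patient trait predicts attainment (2.B.8): "heavy drinkers (n=42, EtG > 499 ng/mL) with a major depressive disorder attained an average of 1 EtG-negative urine sample during treatment (SE=2.2"), against 5.6 consecutive negative samples in non-depressed participants.

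Attainment rates, relapse hazards and the link between prognosis and relapse are not in the documents. All values for them below are assumptions, and relapse is treated as continuously observed. In both calculations the arm has no effect on anyone's relapse hazard, so the true hazard ratio (HR) is 1.00.

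**Calculation A: two types of attainer.** 80 per arm. Those who would attain in either arm relapse at 0.08 per week. The extra attainers in the modified arm relapse at k times that rate. The horizon is 30 weeks, with a log-rank test. With attainment p0 and p1, the ratio of average hazards at the start is

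1 + [(p1 - p0)/p1] x (k - 1).

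For 35% vs 50% and k = 2 this is 1 + (15/50) x 1 = 1.30. The apparent HR over the whole period is smaller, because high-hazard people leave the risk set early.

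| Attainment | k | Starting ratio | Apparent HR | Rejection |
|---|---|---|---|---|
| 35% vs 50% | 1 | 1.00 | 0.99 | 5.7% |
| 35% vs 42% | 1.5-2 | 1.08-1.17 | 1.06-1.11 | 5.7-7.0% |
| 35% vs 45% | 1.5-2 | 1.11-1.22 | 1.09-1.13 | 5.5-8.1% |
| 35% vs 50% | 2-3 | 1.30-1.60 | 1.19-1.26 | 10-15% |
| 30% vs 55% | 2-3 | 1.45-1.91 | 1.3-1.4 | 16-26% |

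**Calculation B: a continuous prognostic factor.** U is standard normal, logit P(attain) = a(arm) - cU, and the relapse hazard is 0.25 x exp(gU) per month over 9 months. Cox regression is fitted among attainers only, with 20,000 randomized per arm so that the HR shows bias rather than sampling noise.

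| Attainment | c=0.7, g=0.35 | c=1, g=0.7 | c=2, g=1 |
|---|---|---|---|
| 30% vs 40% | 1.02 | 1.05 | 1.14 |
| 30% vs 50% | 1.05 | 1.11 | 1.21 |
| 30% vs 60% | 1.09 | 1.16 | 1.37 |

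With equal attainment (30% in both arms) the HR is 0.95-1.01. When U does not affect attainment (c = 0) it is 0.99-1.03. Both are simulation noise around 1.

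At 80 per arm (500 runs):
- 30% vs 50%, c=1, g=0.7: about 65 of 160 people analysed (expected 24 + 40 = 64). The arm with more attainment has HR above 1 in 66% of runs; rejection is 6.6%.
- 30% vs 60%, c=2, g=1: about 72 of 160 analysed (24 + 48 = 72). HR is above 1 in 85% of runs; rejection is 13.8%.

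**The same data with everyone included.** Counting never-attainers as relapsed at about time zero, the HR across 30% vs 40-60% runs from 0.92 to 0.72, in favour of the arm with more abstinence. Mean abstinent time per randomized person is, for example, 1.37 vs 2.17 months (30% vs 50%, c=1, g=0.7). The apparent direction depends on whether never-attainers are counted.

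**Observation after treatment.** From week 20 the gaps between EtG samples are 25 - 20 = 5, 33 - 25 = 8 and 47 - 33 = 14 weeks, while the Specific Aims put EtG detection at up to 5 days. Relapse in follow-up can be dated only coarsely, in any population.

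**The case against.** **The plan never says that the comparison is restricted to attainers.** True. A reader might infer that the plan knowingly chose an attainer-only Cox analysis. The documents do not support that: no model is tied to this measure, and the next paragraph claims all 240. What stands is that the outcome's definition excludes never-abstinent people and nothing brings them back. The Missing Data methods address values that were not observed, not an outcome that never came into being.

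**The bias is not automatic.** Also true. It is tempting to say that the compared groups differ in prognosis by construction, or that the analysis always penalizes the arm that starts more abstinence. Both calculations give an HR of about 1 when no factor is shared between attainment and relapse. Section 2.B.8 supports a link between depression and attaining abstinence; nothing in the documents shows a link with relapse afterwards. Aim 4 makes the recruitment of harder cases plausible, not certain.

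**Covariates may help.** Section 4.G.2 adjusts for variables that differ between groups and for baseline measures related to the outcome, and mood, craving, cognition and motivation are all measured. This could remove part of the bias, and neither calculation adjusts for anything. But a balance check on the randomized groups does not show an imbalance that arises only among attainers, and unmeasured traits remain.

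**It is a minor measure.** It is the fifth item in an illustrative list. Use over time, longest duration and time to first abstinence can all be defined for everyone randomized, and would give context to a discordant relapse result. This limits the consequence but does not make the relapse test valid.

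**Conclusion.** The point holds in limited form and should be corrected. As written, a superiority comparison is planned on an outcome that exists only in a post-randomization subset, and this cannot be reconciled with the stated sample of 240. That part follows from the text and needs no assumption.

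The size of any bias does rest on assumptions: different attainment by arm, and a prognostic factor that affects both attainment and relapse and is not fully adjusted for. Under modest to moderate settings the distortion is small to moderate (HR about 1.05-1.2, rejection about 6-10% against a nominal 5%). Values near HR 1.4 and 25% need a 25-point difference in attainment and extra attainers who relapse at three times the hazard. These are illustrations, not forecasts for this trial.

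A reader might also infer that the trial's main conclusion is at risk. It is not: the primary outcome is EtG-verified abstinence over time in all randomized participants and does not condition on becoming abstinent.

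**What to change.** 1. Report time to relapse among attainers descriptively by arm, with the number attaining in each arm. Make no between-arm test and no causal claim. State the required abstinence period, the time origin and the definition of relapse.
2. Base between-arm inference on maintenance on an outcome defined for all 240. The already listed longest duration of abstinence serves, with zero for never-attainers. Compute it over weeks 9-20, where there are 12 x 3 = 36 scheduled samples and all arms are reinforced for abstinence only. State how a missing sample within a run is handled.
3. Analyse weeks 25, 33 and 47 separately, as point abstinence at each visit. A weekly sustained-abstinence time running into follow-up would not be observed.

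The cost is a change to the analysis plan and some recoding, with no new data, visits or participants. The drawback is that the all-randomized outcome mixes starting abstinence with keeping it, so it cannot isolate an effect on relapse alone. The report should say so.

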Because the **primary barrier to CM implementation is related to cost**, we will conduct a cost-benefit and cost-effectiveness analysis to assess the relative economic viability of each CM intervention. [Finally, little is known about moderators of outcomes in CM because past studies focused on moderators in isolation, without a theoretical model. We will use the NIAAA Addictions Neuroclinical Assessment (ANA) framework to determine how its 3 domains – **executive functioning, negative emotionality, and alcohol-related incentive salience – predict treatment outcomes across CM adaptations.**] This study promises to have a high impact because it will determine if CM adaptations can improve outcomes and reduce costs, and identify moderators of CM efficacy in a high-cost, complex, and understudied population. Our **Specific Aims** are to:

1. Determine whether levels of alcohol abstinence during the last 3 months of treatment and a 6-month follow-up period vary by CM condition. *We hypothesize that participants in the 2 modified CM conditions will attain higher rates of abstinence than those in the Usual CM condition.*
2. Determine whether randomization groups differ on secondary alcohol outcomes, drug use, psychiatric severity, HIV risk behavior, and cigarette smoking. *We hypothesize that participants in the 2 modified CM conditions will attain better outcomes than those in the Usual CM condition.*
3. Conduct cost-benefit and cost-effectiveness analyses to determine the relative economic viability of the 3 CM conditions. *We hypothesize that the 2 modified CM conditions will dominate the Usual CM group, and the Shaping CM condition will be the most cost-effective.*
4. [Identify ANA-based moderators of CM treatment response across the sample and within CM conditions. *We hypothesize that higher executive dysfunction, negative emotionality, and alcohol-related incentive salience will be associated with lower levels of alcohol abstinence across all CM conditions. We also hypothesize that participants with higher levels of these characteristics will be more likely to respond to the modified CM conditions than to the Usual CM condition.*]

**Table 1.** Mean number of consecutive alcohol-negative samples

	CM M (SD)	Control M (SD)
EtG < 500 ng/mL	11.6 (10.7)	4.9 (3.5)
EtG > 499 ng/mL	4.6 (6.9)	3.7 (7.3)

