Executive functioning: NIH Toolbox/MCQ (cognitive tests/self-report)	✓			
Alcohol incentive salience (self-report/cognitive tests)	✓			
Adverse Events				
Alcohol withdrawal: SHOT (interviewer rating)	✓	3x / Wk	3x / Wk	Every visit
Participant safety (self-report/observation)	✓	3x / Wk	3x / Wk	Every visit

**4.F.2 Measures Overview.** Baseline data will include assessment of eligibility criteria and measures for Aims 1-4. Our primary outcome (Aim 1) is biochemically confirmed alcohol abstinence, measured 3 times per week during the final 12 weeks of the treatment period (weeks 9-20) and 3 times total during the 6-month follow-up period. Aim 2 outcomes will be collected in a similar fashion. Cost data will be collected for 12 months before and after randomization. Aim 3 outcomes consist primarily of self-reported use of non-study

healthcare resources, QALYs, days of alcohol abstinence, and heavy drinking days averted. We will collect data on each ANA domain to test for predictors of alcohol abstinence during CM interventions.

**4.F.3 Eligibility Criteria.** Age and frequency of recent drinking will be assessed by phone screening. The Structured Clinical Interview for DSM-5 (SCID-5) interview, clinical trials version, will be administered to assess diagnostic inclusion (SMI, AUDs) and exclusion criteria. Competency to provide informed consent will be assessed as described in Section 4.C.2.

**4.F.4 Primary Outcome.** Our primary outcome will be alcohol abstinence during the last 3 months of treatment and the 6-month follow-up period. At each study visit, urine samples will be collected and analyzed onsite for EtG by using the [commercially available Diagnostic Reagents Incorporated EtG immunoassay on an Indiko Bench Top Analyzer (ThermoFischer Scientific, Freemont, CA).] We will use the assay to create a binary indicator of alcohol use defined by EtG < 100 ng/mL. That threshold was used in our first funding period and in our ongoing CM trials. While it is not associated with false positives due to non-beverage alcohol exposure, we will ask participants to abstain from using all alcohol-containing products, like hand sanitizer.

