**Aim 3.** We will conduct a systematic economic evaluation of the 3 CM conditions. We will estimate the relative economic value of each intervention by conducting cost-benefit and cost-effectiveness analyses. The economic evaluation will follow the guidelines recommended by the **Panel on Cost Effectiveness in Health and Medicine**, Glick et al. and Drummond. Cost-benefit analyses will entail determining the costs of each condition and extrapolating the downstream savings resulting from reduced alcohol consumption and reduced alcohol-related consequences relative to Usual CM, at which point the estimated net benefit of each condition can be compared. The primary outcome will be the incremental cost-effectiveness ratio (ICER), which will be the incremental cost of one CM condition relative to another, divided by the incremental effectiveness of one CM condition relative to another. The most cost-effective condition will be identified by using the rules of dominance and extended dominance. The primary economic effectiveness outcome in the denominator of each ICER will be the QALY, a measure that incorporates both duration and health-related quality-of-life, and is **recommended as the primary effectiveness outcome measure** for economic evaluation studies by the Panel on Cost Effectiveness in Health and Medicine. In addition to capturing a wider range of consequences than clinical effectiveness measures, QALYs permit comparisons across diseases and interventions, enabling broader economic interpretation. In addition, generally accepted cost-effectiveness thresholds for defining value have been established for QALYs, but not for clinical measures. Nevertheless, **we will also calculate ICERs by using** the clinical effectiveness measures of **duration of alcohol abstinence**, to permit comparisons with existing economic evaluations of CM interventions that relied on measures of abstinence, and **number of heavy drinking days averted** a clinically significant alcohol outcome measure.

Analyses will be conducted from the perspectives of the payer of healthcare services (i.e., the insurer), the treatment provider, and society. The payer and provider represent important perspectives, given the pivotal role played by each in sustaining the intervention, while the societal perspective is recommended as the

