appropriate reference case. All values will be adjusted for inflation. Since no follow-up measurements will be taken beyond 12 months following baseline, discounting for time preference will not be required. Given the differences in mechanisms to generate data, separate multivariable generalized-linear models (GLMs) will be estimated to predict the mean value of each resource category at each time point. GLMs permit us to choose the most appropriate mean and variance functions according to fit with the data. A multivariable GLM will also be used to predict health-related quality of life preference weights for each participant at each time point. QALYs gained by the intervention will then be estimated by using the area under the curve. The method of recycled predictions will be used to obtain the final predicted mean values for each study group and resource, which will then be summed and tested according to the relevant perspective. To account for sampling uncertainty in point estimates, both the p-values and standard errors, as well as the confidence intervals for the ICER, will be estimated by using nonparametric bootstrapping techniques within the multivariable framework. Parametric methods based on parameters obtained from bootstrapping will be used to estimate acceptability curves, which illustrate the probability that the intervention is a good value for different willingness-to-pay thresholds (e.g., cost-per-QALY). Sensitivity analyses will be performed to account for uncertain precision in assumptions and parameter estimates applied in the analysis.

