**Aim 3 Power Analysis.** Power analyses for cost-effectiveness analyses are based on assumptions regarding differences in cost and effect, standard deviations of cost and effect, the correlation of the difference in cost and effect, desired confidence and power levels, and the maximum willingness-to-pay value. Using a range of values for each of these factors, as well as the target sample size of 180 (60 per group), we estimated the power for the primary outcomes of these analyses: cost per QALY, cost per abstinent year, and cost per heavy drinking day averted. We estimate at least 80% power to be 95% confident that an intervention is a good value at the commonly cited lower-bound willingness-to-pay threshold of \$50,000 per QALY. Power for the cost-benefit analysis is more speculative. However, if the intervention cost is \$396 (SD=\$41) and there is a cost offset of \$1,000 from reductions in use of high-cost healthcare services, the net benefits would be \$604. To achieve 80% power, the standard deviation of the cost offset would have to be less than \$1,650. While difficult to forecast, it is not unreasonable to have a standard deviation less than 165% of the mean cost offset. Hence, we should have sufficient power for our cost-benefit analysis.

**Aim 4 Power Analysis.** For binary outcomes (e.g., submissions of EtG-negative samples), our trial will have at least 81% power to detect a 10% difference across the moderator (e.g., executive functioning) by group interactions. We will also maintain at least 80% power to detect a 13% difference in binary outcomes in our simple effects analysis or linear trend analysis to probe the interaction further. For continuous outcomes, our trial will have at least 80% power to detect a 30% mean reduction in continuous alcohol use measures (e.g., heavy drinking days) across the moderator (e.g., executive functioning) by group interactions. We will also have at least 82% power to detect a 44% mean reduction in continuous alcohol use measures (e.g., heavy drinking days) when conducting our simple effects analysis or linear trend analysis to probe the interaction further. Our planned analyses for Aim 4 provide sufficient power for nearly every scenario, even with a conservative estimate, because our missing data strategy will help to recover much of the lost power.]

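### Aim 3 puts its primary confidence interval on a cost-per-QALY ratio that loses its ordering if the hypothesised dominance occurs; net monetary benefit from the same bootstrap would not

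*Combined protocol and SAP*

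**What the plan says.** Section 4.G.2 (Aim 3) of the combined protocol and SAP names the ratio as the main economic result: "The primary outcome will be the incremental cost-effectiveness ratio (ICER"). It then fixes the denominator: "The primary economic effectiveness outcome in the denominator of each ICER will be the QALY". On uncertainty it says that p-values and standard errors, "as well as the confidence intervals for the ICER, will be estimated by using nonparametric bootstrapping techniques within the multivariable framework".

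The Aim 3 hypothesis in Section 1 is that "the 2 modified CM conditions will dominate the Usual CM group". Section 2.C adds that Shaping CM is expected to dominate the other conditions.

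The same part of Section 4.G.2 also plans to pick the most cost-effective condition by dominance and extended-dominance rules, and to draw acceptability curves over willingness-to-pay. A net benefit is mentioned there, but only for the cost-benefit analysis (savings less cost). No QALY-based net monetary benefit is defined. Nothing says how a negative ICER, or bootstrap replicates scattered over several quadrants of the cost-effectiveness plane, will be reported.

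Section 4.G.3 (Aim 3 power) says "We estimate at least 80% power to be 95% confident that an intervention is a good value" at a threshold of $50,000 per QALY, with 60 per group.

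**The concern.** A ratio of differences works as a summary only when both differences have the same known sign. If a modified arm is cheaper and better, as hypothesised, the ICER is negative and its size says nothing about how good the arm is. The arm that is dearer and worse has a negative ICER too.

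If the QALY difference is not clearly away from zero, bootstrap replicates fall on both sides of a zero denominator. An interval formed by sorting the ratios then mixes replicates with opposite meanings. Follow-up ends within 12 months of baseline, which limits how large a QALY difference can be.

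At stake is whether the interval attached to the primary economic outcome can tell a reader how much better or worse one CM condition is, and with what precision.

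**Working it through.** **1. The plan's own Aim 3 figures.** The 80% power for cost per QALY cannot be reproduced or refuted, because Section 4.G.3 prints no QALY difference, QALY SD, total-cost SD or correlation. The one Aim 3 calculation with printed inputs is the cost-benefit illustration: $1,000 offset - $396 intervention cost = $604 net, with an SD limit of $1,650 for 80% power. As a one-sample test with n = 60, z = 604 / (1,650/√60) = 604/213.0 = 2.836, and power = Φ(2.836 - 1.96) = 81%. It reproduces in that form. Using $604 and $1,650 as a between-arm cost difference and a per-person cost SD is therefore an assumption made here, not the plan's statement.

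**2. Ordering. No SD is needed.** ICER = ΔC/ΔQ and net monetary benefit NMB = 50,000 × ΔQ - ΔC.

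| ΔC | ΔQ | ICER | NMB |
|---|---|---|---|
| -$604 | +0.02 | -$30,200 | +$1,604 |
| +$604 | -0.02 | -$30,200 | -$1,604 |
| -$604 | +0.01 | -$60,400 | +$1,104 |
| -$604 | +0.05 | -$12,080 | +$3,104 |

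The first two rows are opposite conclusions with the same ratio. For a fixed saving, a larger health gain moves the ratio towards zero.

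**3. Interval, under assumptions.** Inputs: 60 per arm (Section 4.G.3); ΔC = -$604 and cost SD $1,650 (borrowed as in step 1); correlation 0, ΔQ and QALY SD (assumed). The plan does not name the type of bootstrap interval; percentile limits are assumed. Estimates are set at their assumed true values, and normal draws stand in for bootstrap replicates. Repeat runs move the outermost limits by up to about $10,000.

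- SE(ΔC) = 1,650 × √(2/60) = $301.
- SE(ΔQ) = SD × √(2/60) = 0.0183 at SD 0.10 and 0.0365 at SD 0.20.
- SE(NMB) = √(301² + (50,000 × SE(ΔQ))²) = $961 and $1,850.
- Share of replicates with a QALY loss = Φ(-ΔQ/SE(ΔQ)).

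| ΔQ | QALY SD | QALY loss | ICER limits | NMB (95% limits) |
|---|---|---|---|---|
| 0.02 | 0.10 | 14% | about -$310,000 to +$265,000 | $1,604 (-$280 to $3,488) |
| 0.02 | 0.20 | 29% | about -$235,000 to +$220,000 | $1,604 (-$2,023 to $5,231) |
| 0.04 | 0.10 | 1% | about -$84,000 to +$2,000 | $2,604 ($720 to $4,488) |
| 0.09 | 0.20 | 1% | about -$30,600 to +$300 | $5,104 ($1,477 to $8,731) |

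In the first two rows, doubling the QALY SD narrows the ICER interval from about $575,000 to $455,000 wide, while the NMB interval widens from $3,768 to $7,254. Only the second responds to noise as an interval should.

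**4. Which gains fit the stated power?** For 80% two-sided power on NMB, ΔQ = (2.80 × SE(NMB) - 604)/50,000. That is 0.042 at SD 0.10 and 0.092 at SD 0.20, so the last two rows are close to the plan's premise. A gain of 0.02 has power of only about 39% at SD 0.10 (Φ(1,604/961 - 1.96)) and 14% at SD 0.20. Even at 0.042 and 0.092, the 95% interval for the QALY difference would include zero in about 37% and 29% of trials, and a Fieller interval for the ratio would then be unbounded.

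**5. If an arm costs more.** With ΔC = +$500, ΔQ = 0.02 and QALY SD 0.20, about 90% of draws have an ICER below $50,000 but only 61% have positive NMB. The gap is mainly draws that cost more and lose QALYs, whose negative ratio passes the threshold. With ΔC = +$500, ΔQ = 0.05 and SD 0.10 the limits are about -$2,200 to +$40,500, which is close to an ordinary ICER result.

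**The case against.** The best defence is that the plan does not rest its economic conclusion on the ICER interval alone. Dominance and extended-dominance rules identify the preferred condition, and they exist for the cheaper-and-better case. Summed costs are tested in their own right. The acceptability curve read at $50,000 is the probability that net monetary benefit is positive. All of this stands. A reader might infer that Aim 3 as a whole cannot be interpreted; the documents do not support that.

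Three other inferences also go too far:

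- That the power statement contradicts the primary outcome. It is cost per QALY judged against a threshold, which shows that a threshold decision was already intended.
- That limits of several hundred thousand dollars are what the plan implies. They need the assumed 0.02 gain, which falls far short of the stated 80% power.
- That the ratio must fail. Dominance is a hypothesis, and Table 3 gives High-Magnitude CM an expected payout of $1,000 against $500 for Usual CM. A positive cost difference with a clear QALY gain yields a usable ICER.

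What the defence does not answer: the dominance rules carry no stated measure of uncertainty, and an acceptability curve gives a probability, not an effect size with an interval. The interval the plan ties to its primary outcome is the one on the ratio.

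**Conclusion.** The point holds in a confined form. If the plan's own hypothesis is true, the ICER is negative and unordered whatever the sample size. If the QALY difference is not clearly above zero, its percentile interval mixes quadrants. The first part is arithmetic and needs no assumption. The size of the second depends on a QALY gain, SDs and a correlation that the documents do not give: very wide limits at a gain of 0.02, and bounded but mostly negative limits at gains near 0.04 to 0.09 that would match the stated power. The defect lies in the choice of the ICER interval as primary inferential quantity and in the missing reporting rule. It should be corrected before outcome data are seen, but it does not invalidate Aim 3.

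**What to change.** In Section 4.G.2 (Aim 3):

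- Make incremental net monetary benefit at $50,000 per QALY (the threshold already used in Section 4.G.3), with its bootstrap confidence interval, the primary inferential result for each pair of arms. Show it beside the planned acceptability curve, which covers other thresholds.
- Report the ICER as a point estimate when the cost and QALY differences have the same sign, and state the quadrant. When the signs differ, state in words which arm dominates.

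The cost is a small change of SAP wording. The same bootstrap output serves and no data are added.

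Naming EQ-5D before randomization and prior cost as covariates would be a useful but secondary clarification. The data are planned ("Cost data will be collected for 12 months before and after randomization"), and the general covariate rule at the start of Section 4.G.2 already adjusts for baseline measures related to the outcome.
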